13.2 Data Coordinating Center/Biostatistician Responsibilities

Data collection is the responsibility of the study site staff at the participating clinical site under the supervision of the Investigator. During the study, the Investigator must maintain complete and accurate documentation for the study.

The statistical and data coordination center for this study will be responsible for data management, quality review, analysis, and reporting of the study data.

13.3 Data Capture Methods

Clinical (including AE/SAEs, concomitant medications, medical history, and physical assessments) and clinical laboratory values will be collected on data collection forms by study personnel then entered into eCRFs via a 21 CFR Part 11-compliant internet data entry system provided by PPD. The data system includes password protection and internal quality checks, such as automatic range checks, to identify data that appear inconsistent, incomplete, or inaccurate.

13.4 Types of Data

Data for this trial will include clinical, safety, and outcome measures.

13.5 Study Records Retention

Study records and reports must be maintained for a minimum of 2 years after a marketing application is approved for AV-1 for the indication for which it is being investigated; or, if no

application is to be filed or if the application is not approved for AV-1, until 2 years after the investigation is discontinued and the FDA has been notified. These documents will be retained for a longer period, however, if required by local regulations. Informed consent forms will be maintained as long as the sample/specimen exists.

No records will be destroyed without the written consent of the Sponsor. It is the responsibility of the Sponsor to inform the Investigator when these documents no longer need to be retained.

13.6 Protocol Deviations

The Investigator or designee must document and explain in the subject's source documentation any deviation from the approved protocol. The Investigator may implement a deviation from, or a change to, the protocol to eliminate an immediate hazard to study subjects without prior IRB approval. As soon as possible after such an occurrence, the implemented deviation or change, the reasons for it, and any proposed protocol amendments should be submitted to the IRB for review and approval, to the Sponsor Representative for agreement, and to the regulatory authorities, if required.

A protocol deviation is any change, divergence, or departure from the study design or procedures defined in the protocol. An important deviation (sometimes referred to as a major or significant deviation) is a subset of protocol deviations that leads to a subject being discontinued from the study, or significantly affects the subject's rights, safety, or well-being or the completeness, accuracy, and reliability of the study data. An important deviation can include nonadherence to inclusion or exclusion criteria or nonadherence to FDA regulations or ICH E6(R2) guidelines.

Protocol deviations will be documented by the clinical monitor throughout the course of monitoring visits. The Investigator will be notified in writing by the monitor of deviations. The IRB should be notified of all protocol deviations, if appropriate, in a timely manner.

14 CLINICAL MONITORING

Site monitoring is conducted to ensure that the human subjects' protections, study and laboratory procedures, study intervention administration, and data collection processes are of high quality and meet Sponsor, ICH/GCP guidelines and applicable regulations, and that this trial is conducted in accordance with the protocol and applicable standard operating procedures. PPD, the Sponsor, or its designee will conduct site-monitoring visits as detailed in the clinical monitoring plan.

Site visits will be made at standard intervals as defined by the Sponsor and may be made more frequently as directed by the Sponsor. Monitoring visits will include, but are not limited to, review of regulatory files, accountability records, eCRFs, ICFs, medical and laboratory reports, and protocol and GCP compliance. Site monitors will have access to the clinical site, study site staff, and all study documentation according to the Sponsor-approved site monitoring plan. Study monitors will meet with the Investigator to discuss any problems and actions to be taken and will document clinical site visit findings and discussions.

15 PUBLICATION POLICY

Following completion of the study, the Sponsor is expected to publish the results of this research in a scientific journal. All Investigators funded by the NIH must submit or have submitted for them to the National Library of Medicine's PubMed Central (http://www.ncbi.nlm.nih.gov/pmc/) an electronic version of their final, peer-reviewed manuscripts upon acceptance for publication, to be made publicly available no later than 12 months after the official date of publication. The NIH Public Access Policy ensures the public has access to the published results of NIH funded research. It requires the Investigators to submit final peer-reviewed journal manuscripts that arise from NIH funds to the digital archive PubMed Central upon acceptance for publication. Further, the policy stipulates that these papers must be accessible to the public on PubMed Central no later than 12 months after publication.

Refer to:

- NIH Public Access Policy, http://publicaccess.nih.gov/
- NIH Office of Extramural Research Grants and Funding, http://grants.nih.gov/grants/oer.htm

As of January 2018, all clinical trials supported by the NIH must be registered on ClinicalTrials.gov, no later than 21 days after the enrollment of the first subject. Results of all clinical trials need to be submitted no later than 12 months following the primary completion date. A delay of up to 2 years is available for trials that meet certain criteria and have applied for certification of delayed posting.

As part of the result posting a copy of this protocol (and its amendments) and a copy of the statistical analysis plan will be posted on ClincialTrials.gov.

For this trial the responsible party is AbViro which will register the trial and post results.

The responsible party does not plan to request certification of delayed posting.

Refer to:

- Public Law 110-85, Section 801, Clinical Trial Databases
- 42CFR11
- NIH NOT-OD-16-149

17 APPENDICES

17.1 Appendix A. Schedule of Events

Ph	Phase Screening Check-in				EOS/ ET										
Procedure ^(a)	Day	-35 to −2	-1	1	2	3	5	8 (+2)	15 (±2)	22 (±2)	29 (±2)	43 (±3)	57 (±3)	85 (±5)	120 (±5)
Admission to clinic			X				s .		278			, ,		6 3	
Discharge from clinic(b)							X		200					6	38
Outpatient visit							46	X	X	X	X	X	X	X	X ^(c)
Informed consent		X							5.8						38
Demographics		X							5.8						38
Serology ^(d)		X							5.8						38
Flavivirus serology test(e)		X							5.8						38
Serum FSH ^(f)		X							5.8						38
Inclusion/exclusion criteria		X	X						5.8						38
Medical history(g)		X	X				X	X	X	X	X	X	X	X	X
Height, weight, and BMI(h)		X	X						5.8					X	X
Physical examination(i)		X	X				X	X	X	X	X	X	X	X	X
Vital sign measurements(i)		X	X	X	X	X	X	X	X	X		X		X	X
12-lead ECG(k)		X		X	X			X	5.8			X		X	X
Clinical laboratory testing(1)		X	X	X		X		X	X	X		X		X	X
Urine drug ^(m)		X	X						5.8	X		X		X	38
Urine cotinine testing			X						338						38
Pregnancy test ⁽ⁿ⁾		X	X						1.8						38
Randomization(o)				X					1.8						38
AV-1 or placebo administration ^(p)				X					3)						9) 9
PK blood sample collection(q)				X	X	X	X	X	X	X	X	X	X	X	X
Anti-AV-1 antibody blood sample			X						38		X			X	X
collection			8				8		us.		Λ	8 8		A	Λ
Hypersensitivity panel collection(r)	į		X	X	X		ž							2 9	
Fasting period ^(s)	į		X	X			ž							2 9	
Non-fasting period(t)		j.			X	X	X		100						

	Phase	Screening	Check-in		Treatment Period					EOS/ ET					
Procedure ^(a)	Day	-35 to −2	-1	1	2	3	5	8 (+2)	15 (±2)	22 (±2)	29 (±2)	43 (±3)	57 (±3)	85 (±5)	120 (±5)
Solicited AEs, Unsolicited AEs, and SAEs ^(u)				+						X —	-81 -10				-
Prior/concomitant medications			•						X -		- 8	leg-	B 8		

Abbreviations: AEs, adverse events; BMI, body mass index; ECG, electrocardiogram; EOS, end of study; ET, early termination; FSH, follicle-stimulating hormone; IP, investigational product; PK, pharmacokinetic; QTcF, QT interval corrected for heart rate using Fridericia's formula; SAE, serious adverse event. Notes:

- (a) When procedures overlap or occur at the same time point, they should be performed in the following order: ECG, vital signs, then PK sampling which should be timed to occur last and as close to the scheduled time window as possible.
- (b) Discharge from the clinical site on Day 5 after all study related activities are completed.
- (c) The final follow-up visit will occur on Day 120 (approximately Week 17).
- (d) Serology testing will include hepatitis B surface antigen, hepatitis C virus antibody, and human immunodeficiency virus antibody types 1 and 2.
- (e) Flavivirus testing will include dengue, Zika, and West Nile viruses.
- (f) Females only. A serum FSH test may be performed at Screening to confirm postmenopausal status along with at least 12 months of amenorrhea.
- (g) Interim medical history will be done after initial thorough medical and medication history taken at Screening. Any new disorders after dosing on Day 1 will be recorded as an AE.
- (h) Height and weight will be measured, and BMI will be calculated at Screening only. Only weight will be measured at Check-in (Day -1) and on Days 85 and 120.
- (i) A full physical examination will be performed at Screening (skin, head, ears, eyes, nose, throat, neck, thyroid, lungs, heart, cardiovascular, abdomen, lymph nodes, and musculoskeletal system/extremities). Focused examination (lungs, cardiovascular, abdomen, skin) will be performed at Check-in (Day -1) and on Days 5, 8, and 15. Targeted, symptom-directed physical examination will be performed at all other time points.
- Vital signs will be measured at Screening and Check-in; within 60 minutes prior to start of the IP infusion; at 0.5, 1 (±10 minutes), 2, 4, 8, 24, and 48 hours after the start of the IP infusion; and on Days 5, 8, 15, 22, 43, 85, and 120. Vital signs will be measured after the subject has been in the seated or supine position for at least 5 minutes. Vital signs will include systolic and diastolic blood pressure, oral body temperature, heart rate, and respiratory rate.
- (k) Single 12-lead ECG recordings will be made at Screening, within 60 minutes prior to the start of the IP infusion; at 1 (±10 minutes), 2, 4, 8, and 24 hours after the start of the IP infusion; and on Days 8, 43, 85, and 120. Electrocardiograms will be recorded after the subject has been in the supine position for at least 10 minutes. A single repeat measurement is permitted at Screening for eligibility determination. Measurements of the following intervals will be reported: RR interval, PR interval, QRS width, QT interval, and QTcF. Assessments should include comments on whether the tracings are normal or abnormal; rhythm; presence of arrhythmia or conduction defects; morphology; any evidence of myocardial infarction; or ST-segment, T-wave, and U-wave abnormalities.
- (l) Clinical laboratory testing will occur at Screening, Check-in, predose (within 60 minutes) and 48 hours after the start of the IP infusion on Day 1; and on Days 8, 15, 22, 43, 85, and 120. A complete list of assessments is provided in Section 7.2. Blood and urine samples will be collected under fasted conditions and prepared per the clinic's standard procedures.
- (m) Urine drug screen will occur at Screening and Check-in and on Days 22, 43, and 85 per the clinic's standard procedures and per Section 7.2.

- (n) Women of childbearing potential only. A serum pregnancy test will be performed at Screening and Check-in, and tests must be negative prior to enrollment and dosing, respectively.
- (o) After verification of eligibility, subjects will be randomly assigned before dosing on Day 1.
- (p) The start of the IP infusion will be called "0" hour and is denoted with grey shading. All doses of the IP will be administered intravenously over a period of 60 minutes. Subjects will maintain an upright (ie, seated or standing) position for at least 4 hours after the end of infusion.
- ^(q) Blood samples for PK analysis of AV-1 in serum will be collected predose (within 15 minutes); at 0.5, 1 (end of infusion), 1.25, 1.5, 2, 3, 4, 6, 8, 12, 24, and 48 hours after the start of infusion, Day 5 prior to discharge, and at the follow-up visits on Days 8, 15, 22, 29, 43, 57, 85, and 120 (or ET).
- A blood sample will be drawn on Day –1 and tested only if a suspected hypersensitivity reaction occurs during or following infusion on Day 1 at the discretion of the Investigator in consultation with the Sponsor. At the discretion of the Investigator, an additional blood sample will be drawn as soon as possible after the event occurs (Day 1) and again the following day (Day 2).
- (s) During fasting periods, subjects should have nothing to eat or drink except water from 10 hours prior to start of the IP infusion until 4 hours after the end of infusion.
- (t) During non-fasting periods when subjects are at the clinical site, subjects should receive standardized meals per the clinic's standard procedures that are scheduled at the same time in each treatment period during the study.
- (u) Solicited AEs will be assessed from the start of IP infusion until Day 8 and unsolicited AEs will be assessed from the start of IP infusion through the final follow-up visit on Day 120. All AEs should be followed until they are resolved, stable, or judged by the Investigator to be not clinically significant.

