7.1.1 Vital Signs

Vital sign measurements will include systolic and diastolic blood pressure, oral body temperature, heart rate, and respiratory rate. The subject will have rested comfortably in a seated or supine position for at least 5 minutes before all measurements are taken. For time points when ECGs and vital signs occur at the same time point, it is acceptable to perform the vital sign measurements approximately 2 minutes after the ECG as long as the subject remains resting in the supine position. Additional vital signs may be measured for safety of the subjects at the discretion of the Investigator. All measurements will be recorded in the subject's eCRF.

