7.1.2 Twelve-lead ECG

Twelve-lead ECG recordings will be obtained after the subject has rested comfortably in a supine position, for at least 10 minutes. The Investigator should review and sign the ECG for any immediate issues. Electrocardiogram assessments will include comments on whether the tracings are normal or abnormal, rhythm, presence of arrhythmia or conduction defects, morphology, any evidence of myocardial infarction, or ST-segment, T-wave, and U-wave abnormalities. In addition, measurements of the following intervals will be measured and reported: RR interval, PR interval, QRS width, and QTcF.

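### The upright rule after infusion cannot be met together with the supine ECG rule at 2 h and 4 h, and vital-sign posture is not tied to the predose baseline

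*Protocol*

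**What the plan says.** **Upright rule.** Protocol 17.1, footnote (p), fixes the infusion length: "All doses of the IP will be administered intravenously over a period of 60 minutes". It sets the start of infusion as hour 0, and then adds: "Subjects will maintain an upright (ie, seated or standing) position for at least 4 hours after the end of infusion". SAP Appendix 1 repeats this footnote.

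**ECG posture.** Footnote (k) states: "Electrocardiograms will be recorded after the subject has been in the supine position for at least 10 minutes". Section 7.1.2 says the same: "Twelve-lead ECG recordings will be obtained after the subject has rested comfortably in a supine position, for at least 10 minutes". SAP 10.4 and SAP Appendix 1 repeat the rule. On Days 1 and 2, the post-dose ECGs fall "at 1 (±10 minutes), 2, 4, 8, and 24 hours after the start of the IP infusion".

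**Vital-sign posture.** Section 7.1.1 states: "The subject will have rested comfortably in a seated or supine position for at least 5 minutes before all measurements are taken". Footnote (j) agrees: "Vital signs will be measured after the subject has been in the seated or supine position for at least 5 minutes". Over the first three days the post-dose readings are "at 0.5, 1 (±10 minutes), 2, 4, 8, 24, and 48 hours after the start of the IP infusion". Section 7.1.1 adds that, where an ECG shares the time point, it is acceptable to take vital signs about 2 minutes after it while the subject stays supine. That is permission, not a requirement. SAP 10.3 carries the same choice of posture.

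**Use of the data.** Vital signs and ECG parameters are among the primary safety endpoints (Section 3.3.1). SAP Section 4 takes the last non-missing value before dosing as baseline, and SAP 10.3 and 10.4 summarise change from it. No passage requires one posture throughout or says that posture is recorded.

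**The concern.** There are two separate problems.

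The first is a contradiction. Some ECGs that must be supine are scheduled in a period when the subject must be seated or standing. Staff have to break one instruction to follow the other, and Section 13.6 counts any departure from protocol procedures as a deviation. If staff gave footnote (p) priority, the affected tracings would no longer match the supine predose ECG.

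The second is a gap. A subject's vital signs may be supine at predose and seated later, or the reverse. Any posture effect on heart rate or blood pressure would then enter the change from baseline together with any effect of the infusion. With 6 AV-1 subjects per dose, avoidable variability is unwelcome. One safety rule also uses such a difference for a single person: Section 8.6.2 compares blood pressure during the infusion with the predose value.

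**Working it through.** The plan states no figure on this point, so there is none to reproduce. The check is one of overlapping intervals.

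**Inputs**
- End of infusion, E = 1:00 (hours:minutes after the start), from footnote (p).
- Upright window = [E, E + 4 h] = [1:00, 5:00], from footnote (p). The upper end is a minimum.
- Supine period for an ECG recorded at time t = [t − 0:10, t], from footnote (k) and Section 7.1.2.
- Timing tolerance: ±10 min at 1 h (footnote (k)). The other times carry none in the footnote. I assume ±30 min, from the post-dose allowance in Section 6 for procedures that share a time point.

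**Formula:** overlap = max(0, min(t, 5:00) − max(t − 0:10, 1:00)).

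| ECG | Early: supine period, overlap | Nominal: supine period, overlap | Late: supine period, overlap |
|---|---|---|---|
| 1 h | 0:40–0:50, 0 min | 0:50–1:00, 0 min | 1:00–1:10, 10 min |
| 2 h | 1:20–1:30, 10 min | 1:50–2:00, 10 min | 2:20–2:30, 10 min |
| 4 h | 3:20–3:30, 10 min | 3:50–4:00, 10 min | 4:20–4:30, 10 min |
| 8 h | 7:20–7:30, 0 min | 7:50–8:00, 0 min | 8:20–8:30, 0 min |

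The 24 h ECG is clear of the window. At 2 h and 4 h the whole supine period lies inside it, whatever the timing within tolerance. At 1 h the outcome depends on whether the supine period runs past the end of infusion.

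**Count:** 2 ECGs × 40 planned subjects = 80 scheduled recordings that cannot meet both rules.

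**Sensitivity to infusion length.** Section 8.6.2 allows the rate to be halved from 250 to 125 mL/hour. If that applied from the start, 60 minutes would become 120 and the window would be [2:00, 6:00]. The nominal 2 h supine period (1:50–2:00) would then fall just outside, but the 4 h period (3:50–4:00) would still be inside.

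**Vital signs**
1. Post-dose times: 0.5, 1, 2, 4, 8, 24 and 48 h (7), plus Days 5, 8, 15, 22, 43, 85 and 120 (7), giving 14.
2. Nine share a time with an ECG: 1, 2, 4, 8 and 24 h, and Days 8, 43, 85 and 120. Five do not: 0.5 h, 48 h, and Days 5, 15 and 22.
3. Sharing a time does not fix the posture, because the supine reading after an ECG is only permitted. The predose reading is equally free.
4. The number of post-dose readings that differ in posture from baseline can therefore be anything from 0 to 14 per subject.
5. At 2 h and 4 h a seated reading meets footnote (p). A supine reading, including one taken straight after the ECG, does not.
6. The blood-pressure comparison with predose in Section 8.6.2 applies during the 1-hour infusion. Of the five readings without an ECG, only 0.5 h falls there.

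**The case against.** The strongest reply is that the practical effect is small. A site would probably read an implied exception into footnote (p), lay the subject down for the ECG and carry on. The posture text is the same for AV-1 and placebo, treatment is blinded, placebo is pooled, summaries are descriptive and no hypothesis is tested. Seated vital signs comply with footnote (p), and a 5-minute rest is already required. Most of this stands. It limits the consequence to added variability, but it does not supply the missing exception or tie the readings to the baseline posture.

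A reader might infer more than the documents support:
- **Uncontrolled posture in the ECG data, and so in the QTcF halting criteria.** ECG posture is specified as supine at every recording, predose included. QTcF would be affected only if a site let footnote (p) override that.
- **Five of 14 vital-sign times (36%) at risk.** This treats readings paired with an ECG as necessarily supine, which Section 7.1.1 does not require.
- **Blood-pressure halting affected across follow-up.** The rule applies only during the infusion, and footnote (p) begins only when the infusion ends.
- **Toxicity grades distorted by a mismatch with baseline.** The vital-sign grades in Table 17-2 are absolute cut-offs. A reading's own posture may affect its grade, but a difference from the baseline posture does not enter it.
- **A stated shift in heart rate.** Something like 5 to 10 bpm would be purely an assumption, since the documents give no figure.

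**Conclusion.** The point holds within limits. Footnote (p) and the supine ECG rule are incompatible at 2 h and 4 h in both the protocol and the SAP, affecting 80 planned recordings. At 1 h they conflict only if the supine period runs past the end of infusion. This rests on a 60-minute infusion and on reading footnote (p) as written, without an implied exception.

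Separately, vital-sign posture is left open at every time, so any post-dose reading may differ in posture from baseline. The result is avoidable variability in change from baseline and, at 0.5 h, in the blood-pressure check against predose. No bias between AV-1 and placebo follows from the text, and the size of the effect cannot be derived from it. The point is worth correcting because the measures are primary safety endpoints and the correction is cheap, not because it undermines the trial's conclusions.

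**What to change.** 1. Reconcile footnote (p) with footnotes (j) and (k) and with Sections 7.1.1 and 7.1.2. Carry the result into SAP 10.3 and 10.4 and into footnotes (j), (k) and (p) of SAP Appendix 1. How the rules are reconciled is for the sponsor to decide.
2. In Section 7.1.1 and footnote (j), require each subject's vital signs to be taken in one consistent position at the predose baseline and at all post-dose times. The choice of position is also the sponsor's.
3. Record the position with each vital-sign reading in the eCRF. The documents do not show whether a field for it already exists.

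The cost is a few sentences in the protocol, matching edits to the SAP, at most one eCRF field, and a few minutes of positioning and rest at some time points. Sample size, visit schedule and analysis methods are unchanged.

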17.2 Appendix B. Toxicity Tables

Table 17-1 Toxicity Grading Scales for Clinical Adverse Events and Reactions

Cardiovascular	Mild (Grade 1)	Moderate (Grade 2)	Severe (Grade 3)
Arrhythmia	N/A	Asymptomatic; transient signs; no medical	Recurrent or persistent symptoms; medical
Hemorrhage, Blood Loss*	Estimated blood loss is <100 mL	intervention required Estimated blood loss is ≥100 mL; no transfusion required	intervention required Transfusion required
QTc (Fridericia's correction)	Asymptomatic, QT interval 450 to 479 msec (male) and 460 to 479 msec (female) OR increase in interval <30 msec above baseline	Asymptomatic, QTc interval 480 to 499 msec OR increase in interval 30 to 50 msec above baseline	Asymptomatic, QTc interval ≥500 msec OR increase in interval ≥60 msec above baseline
PR Interval (prolonged)	PR interval 0.21 to 0.25 sec	PR interval >0.25 sec	Type II 2 nd degree AV block OR ventricular pause >3 sec
Respiratory	Mild (Grade 1)	Moderate (Grade 2)	Severe (Grade 3)
Cough	Transient; no treatment	Persistent	Interferes with daily activities
Bronchospasm, Acute	Transient; no treatment; forced expiratory volume 71 to 80% of predicted peak flow	Requires medical intervention; normalizes with bronchodilator; forced expiratory volume 60 to 70% of predicted peak flow	No normalization with bronchodilator; forced expiratory volume <60% of predicted peak flow
Dyspnea	Does not interfere with usual and social activities	Interferes with usual and social activities; no treatment	Prevents daily and usual social activity OR requires treatment
Gastrointestinal	Mild (Grade 1)	Moderate (Grade 2)	Severe (Grade 3)
Nausea	No interference with activity	Some interference with activity	Prevents daily activity
Vomiting	No interference with activity OR 1 to 2 episodes/24 hours	Some interference with activity OR >2 episodes/24 hours	Prevents daily activity OR requires IV hydration OR requires medical intervention
Diarrhea	2 to 3 loose or watery stools OR <400 grams/24 hours	4 to 5 loose or watery stools OR 400 to 800 grams/24 hours	6 or more loose or watery stools OR >800 grams/24 hours OR requires IV hydration OR requires medical intervention
Local Reactions	Mild (Grade 1)	Moderate (Grade 2)	Severe (Grade 3)
Pain	Does not interfere with activity	Repeated use of non-narcotic pain reliever > 24 hours OR interferes with activity	Any use of narcotic pain reliever OR prevents daily activity
Tenderness	Discomfort only to touch	Discomfort with movement or mild discomfort at rest	Significant discomfort at rest
Erythema/Redness**	2.5 to 5 cm	5.1 to 10 cm	>10 cm

Induration/Swelling***	2.5 to 5 cm AND does not interfere with activity	5.1 to 10 cm OR interferes with activity	>10 cm OR prevents daily activity
Systemic Reactions	ystemic Reactions Mild (Grade 1) Moderate (Grade 2)		Severe (Grade 3)
Allergic Reaction	Pruritus without rash	Localized urticaria OR requires oral therapy	Generalized urticaria; angioedema OR anaphylaxis OR requires epinephrine
Headache	No interference with activity	Repeated use of non-narcotic pain reliever >24 hours OR some interference with activity	Significant, any use of narcotic pain reliever OR prevents daily activity OR requires triptans
Fatigue	No interference with activity	Some interference with activity	Significant; prevents daily activity
Myalgia	No interference with activity	Some interference with activity	Significant; prevents daily activity
Systemic Illness	Mild (Grade 1)	Moderate (Grade 2)	Severe (Grade 3)
Illness or clinical adverse event (as defined according to applicable regulations)	No interference with activity	Some interference with activity not requiring medical intervention	Prevents daily activity and requires medical intervention

^{*}Does not include blood loss from study.

^{**}The local reaction should be measured at the greatest single diameter and recorded as a continuous variable in addition to grading.

***Induration/swelling should be evaluated and graded using the functional scale as well as the actual measurement.

Table 17-2 Vital Signs Toxicity Grading

Vital Signs*	Mild (Grade 1)	Moderate (Grade 2)	Severe (Grade 3)
Fever (°C) **	38.0 to 38.4	38.5 to 38.9	39.0 to 40
(°F) **	100.4 to 101.1	101.2 to 102.0	102.1 to 104
Tachycardia - beats per	101 to 115	116 to 130	>130
minute			
Bradycardia - beats per minute***	50 to 54	45 to 49	<45
Hypertension (systolic) - mm Hg	141 to 150	151 to 155	>155
Hypertension (diastolic) - mm Hg	91 to 95	96 to 100	>100
Hypotension (systolic) – mm Hg	85 to 89	80 to 84	<80
Respiratory rate – breaths per minute	17 to 20	21 to 25	>25

^{*}Subject should be at rest for all vital sign measurements.

^{**}Oral temperature; no recent hot or cold beverages or smoking.

^{***}When resting heart rate is between 60 to 100 beats per minute. Use clinical judgement when characterizing bradycardia among some healthy subject populations, for example, conditioned athletes.

Table 17-3 Laboratory Toxicity Grading

Laboratory Tests	Mild (Grade 1)	Moderate (Grade 2)	Severe (Grade 3)
Liver Function Tests – ALT		2.6 – 5.0 × ULN	
increase by factor	$1.1 - 2.5 \times ULN$	$2.6-3.0 \times ULN$	>5.0 × ULN
Liver Function Tests – AST	$1.1 - 2.5 \times ULN$	$2.6 - 5.0 \times ULN$	>5.0 × ULN
increase by factor	1.1 – 2.3 ^ OLN	2.0 – 3.0 × OLIN	>3.0 ^ OLN
Albumin – Hypoalbuminemia g/dL	2.8 - 3.1	2.5 - 2.7	<2.5
Alkaline Phosphatase – ALP			
increase by factor	$1.1 - 2.0 \times ULN$	$>2.0 - 3.0 \times ULN$	>3.0 × ULN
Anion Gap* – mEq/L	N/A	N/A	N/A
Bilirubin (total) – mg/dL	1.1 – <1.6 × ULN	$1.6 - < 2.6 \times ULN$	≥ 2.6 × ULN
Blood Urea Nitrogen mg/dL	27 – 30	31 – 35	> 35
Calcium –			
Hypocalcemia mg/dL	8.0 - 8.4	7.5 – 7.9	7.0 - 7.4
Calcium –	10.5 11.0	11 1 11 5	11 (12 0
Hypercalcemia mg/dL	10.5 - 11.0	11.1 – 11.5	11.6 - 12.0
Creatinine – mg/dL	$1.2 - 1.3 \times ULN$	>1.3 – 1.8 × ULN	>1.8 × ULN
Glucose (fasted) –	50 – 54	40 – 49	30 – 39
Hypoglycemia mg/dL	30 – 34	40 – 49	30 – 39
Glucose (fasted) –			
Hyperglycemia	117 - 127	128 - 142	>143
Fasting – mg/dL			
Potassium – Hypokalemia	3.3 - 3.4	3.1 - 3.2	2.9 - 3.0
mEq/L	3.3 3.1	3.1 3.2	2.9 3.0
Potassium – Hyperkalemia	5.1 - 5.2	5.3 - 5.4	5.5 - 5.6
mEq/L			
Sodium – Hyponatremia mEq/L	129 – 131	127 – 128	122 – 126
Sodium – Hypernatremia	146 - 147	148 - 149	150 - 152
mEq/L	- 1 - 1 - 1 - 1		
Hematology		T	T
WBC increase - cell/mm ³	9,800 - 14,000	14,001 – 19,000	19,001 – 24,000
WBC decrease - cell/mm ³	2,000 - 3,099	1,000 – 1,999	500 – 999
Absolute Neutrophil Count - cell/mm ³	1,000 - 1.499	500 – 999	0 – 499
Hemoglobin Decrease (female)	9.7 – 10.7	8.2 - 9.6	6.7 – 8.1
- gm/dL	9.7 - 10.7	0.2 – 9.0	0.7 - 0.1
Hemoglobin Decrease (male) -	11.7 – 12.7	9.76 – 11.6	7.6 - 9.6
gm/dL			
Platelets Decrease - cell/mm ³	125,000 - 139,000	100,000 – 124,000	<100,000
Coagulation			
Prothrombin Time – increase by factor	>1.0 – 1.2 × ULN	1.2 – 1.4 × ULN	>1.4 × ULN
Activated Partial thromboplastin time – increase by factor	>1.0 – 1.2 × ULN	1.2 – 1.4 × ULN	>1.4 × ULN

Laboratory Tests	Mild (Grade 1)	Moderate (Grade 2)	Severe (Grade 3)
Urine			
Blood**	1+	2+	>2+
Glucose	1+	2+	>2+
Protein	1+	2+	>2+

Abbreviations: ALP, alkaline phosphatase; ALT, alanine transferase; AST, aspartate aminotransferase; ULN, upper limit of the normal range, WBC, white blood cell.

Source: DHHS 2007.

Infusion-related Reactions and Toxicity Grading **Table 17-4**

Mild (Grade 1)	Moderate (Grade 2)	Severe (Grade 3)
Mild transient reaction; infusion interruption not indicated; intervention not indicated.	Therapy or infusion interruption indicated but responds promptly to symptomatic treatment (eg, antihistamines, nonsteroidal anti-inflammatory drugs, narcotics [opioids], intravenous fluids); prophylactic medication indicated for less than or equal to 24 hours.	Prolonged (eg, not rapidly responsive to symptomatic medication and/or brief interruption of infusion); recurrence of symptoms following initial improvement; hospitalization indicated for other clinical sequelae.

Source: Adapted from the National Cancer Institute Common Terminology Criteria for Adverse Events (Version 5.0) for infusion-related reactions.

^{*}Only values above the ULN and below the LLN are considered abnormal.

^{**}For females: In case of menstruation, screening urinalysis must be postponed, but a result should be available prior to Day 1. Hematuria is acceptable for females in menses for the purposes of evaluating study halting criteria and dose escalation.
